6.6.2. Measurement tools: description and rationale for use

The Numerical Pain Scale used to collect input prior to initiation, and at end of treatment, has been validated in dozens of persistent pain conditions and is the most widely used tool in both Scrambler therapy and NMOSD research to date. SF-36 is a patient-reported survey of overall patient health-related quality of life and has been widely used for QoL assessment in chronic conditions, including in NMOSD research.

NOTE: Please see questionnaires in Appendix A.

6.7. Concomitant and Supportive Therapy

The concomitant medications and therapies deemed necessary for the supportive care and safety of the subject are allowed, provided their use is documented in the medical records.

The use of other concurrent investigational drugs or devices for management of pain is not allowed unless approved by the Principal Investigator.

TENS for Neuropathic Pain in NMOSD

Principal Investigator: [name], PhD

6.8. Discontinuation and Withdrawal of Subjects

All patients who initiate protocol intervention will be included in the overall evaluation of tolerability and acceptability (intent-to-treat analysis). All reasons for discontinuation of therapy will be clearly documented in the record.

Unless the subject refuses, follow-up will continue for the planned duration following the study intervention.

6.8.1. Discontinuation of Intervention

The reasons for discontinuation of protocol treatment include:

- Non-compliance with the study protocol; including, but not limited to not using the device more than 75% of the study duration.
- Unacceptable major reaction to electrical stimulation or other major adverse events
- Intercurrent illness or condition that would, in the judgment of the treating investigator, affect assessment of clinical status to a significant degree or require discontinuation of study intervention.
- At subject's own request. Note: The reason for discontinuation from the study must be documented. The patients will be included in the overall evaluation of tolerability and acceptability (intent-to-treat analysis) if any protocol intervention was administered prior to withdrawal.
- Study is closed or cancelled for any reason.

6.8.2. Withdrawal from Study

The reasons for withdrawal from the study include:

- Subject withdraws consent for follow-up.
- Subject is lost to follow-up.
- Study is terminated for any reason.

TENS for Neuropathic Pain in NMOSD

Principal Investigator: [name], PhD

7. Table 3: Patient Event Calendar

Phase	Baseline Screening/Consent	Experimental (Weeks)				Open Label (Weeks)				Follow-up (weeks)	
Time Point (days)	Within 2 weeks	1	2	3	4	5	6	7	8	12	16
Exam/Tests *	Consent, MRI review, Q [#]	AE and weekly pain score assessment, Q				AE and weekly pain score assessment, Q				AE and pain score assessment	AE and pain score assessment

#Q: Questionnaire (SF-36)

TENS for Neuropathic Pain in NMOSD

Principal Investigator: [name], PhD

8. Adverse Events

In over 4000 patients treated and reported to the FDA for approval, published and in-press studies, no significant adverse events have been reported with Scrambler and related TENS units.

8.1. General

Adverse events will be monitored and documented weekly and at termination of final treatment. Any serious adverse events or study violations will be immediately reported to the Primary Investigator and Partners Institutional Review Board (IRB). Study deviations and other adverse events will additionally be reported to the PI immediately, and to the IRB within the IRB's specified time frame. Given that the device has been cleared for marketing for the proposed use,²⁸ no Investigational Device Exemption is needed through the FDA.

Even though this trial includes a blinded experimental phase, given the low risk of adverse events imposed by the trial, it does not rise to the level of requiring a data safety monitoring board.

Information about all intervention-related adverse events, including those volunteered by the subject, discovered by investigator/study personnel questioning, or detected through physical examination, or other means, will be collected, followed, and reported appropriately.

8.2 Reporting Procedures

All intervention-related adverse events will be captured on the appropriate source documents or in a designated database.

The same applies to any adverse event classified as a “serious adverse event;” these will also only be reported if intervention-/study-related.

Any unexpected intervention-related adverse events and serious adverse events will be reported to the IRB per current institutional standards. If an adverse event requires modification of the informed consent, these modifications will be provided to the IRB with the report of the adverse event. If an adverse event requires modification to the study protocol, these modifications will be provided to the IRB as soon as is possible.

TENS for Neuropathic Pain in NMOSD

Principal Investigator: [name], PhD

9. Safety Monitoring

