11.1. Acceptability

Counts and percentages will be used to assess acceptability based on adherence to treatment schedule. We will report the number and percent of patients in each group who are able to complete all treatments. A chi-square test for independence of group by dichotomous outcome will be performed to assess differences between the two groups. In the event that the expected frequencies are < 5 , Fisher's exact test will be performed. While no serious adverse events have been reported with use of Scrambler or other TENS therapies in the NMOSD patient population, the numbers and percent observed for each group will be reported.

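### Sections 8.1 and 8.2 give incompatible rules for serious adverse events judged unrelated, and the protocol is inconsistent on whether unrelated adverse events are captured at all

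*Combined protocol and SAP*

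**What the plan says.** On SAEs, Section 8.1 is unconditional: "Any serious adverse events or study violations will be immediately reported to the Primary Investigator and Partners Institutional Review Board (IRB"). Section 8.2 makes reporting conditional on cause: "these will also only be reported if intervention-/study-related". It then adds a further rule: "Any unexpected intervention-related adverse events and serious adverse events will be reported to the IRB per current institutional standards".

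On adverse events generally, the text points two ways.

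- Without a condition on cause: Section 8.1 opens with "Adverse events will be monitored and documented weekly and at termination of final treatment" and continues "Study deviations and other adverse events will additionally be reported to the PI immediately", with the IRB to follow within its own time frame. Section 6.5.1.1, item 14, repeats the weekly documentation. The event calendar (Section 7, Table 3) lists adverse event assessment in the experimental, open-label and follow-up phases.
- With a condition on cause: the last paragraph of 8.1 concerns "Information about all intervention-related adverse events, including those volunteered by the subject", and Section 8.2 begins "All intervention-related adverse events will be captured on the appropriate source documents or in a designated database".

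On output, Section 11.1 says, in a sentence about serious adverse events, that "the numbers and percent observed for each group will be reported". It names no test for these counts and does not say whether unrelated events are included or which study phase is covered.

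**The concern.** A coordinator who hears of a hospital admission on a weekly call, and whose team considers it unrelated to the device, gets opposite instructions from two adjoining sections. One possible result is that an SAE does not reach the IRB. The trial has no data safety monitoring board, so no second body is in place to notice.

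There is also a statistical side. A sham arm lets one ask whether events are more frequent on active stimulation without settling the cause of each one. That matters in a relapsing disease of the central nervous system treated with long-term immune suppression, where the cause of an individual event can be unclear. If relatedness is decided first and only related events are entered, the per-group counts rest on that decision, and the omitted events cannot be recovered at analysis. The documents give no criteria for relatedness and name nobody to judge it.

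**Working it through.** No stated figure depends on this point, so the check is a comparison of the text.

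**Step 1: the SAE rules**

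| Rule | SAE judged related | SAE judged unrelated |
|---|---|---|
| 8.1 | To the PI and IRB, immediately | To the PI and IRB, immediately |
| 8.2, second paragraph | Reported | Not reported |
| 8.2, third paragraph, qualifiers read as covering SAEs | To the IRB if unexpected, on the institutional timetable | Not required |
| 8.2, third paragraph, qualifiers read as covering adverse events only | To the IRB, on the institutional timetable | To the IRB, on the institutional timetable |

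In the last column the first two rows are incompatible. The third paragraph of 8.2 does not settle the matter, because it can be read either way. It also introduces a second timing rule beside the immediate one in 8.1. No other section says which text takes precedence.

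**Step 2: capture of adverse events**

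| Place | Subject | Relatedness condition |
|---|---|---|
| 6.5.1.1, item 14 | Weekly monitoring and documentation | None |
| Section 7, Table 3 | Assessment in each phase after baseline | None |
| 8.1, opening sentence | Weekly documentation | None |
| 8.1, other adverse events | Reporting to the PI and IRB | None |
| 8.1, last paragraph | Collection, follow-up, reporting | Intervention-related |
| 8.2, first paragraph | Entry in source documents or database | Intervention-related |

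The two conditional statements say that all related events are captured; neither says that unrelated events are left out. However, the SAE sentence that follows in 8.2 extends the same treatment to SAEs with the words also and only, which implies that its author read the preceding rule as a restriction. Capture is therefore unresolved.

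**Step 3: the effect on Section 11.1**

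If the unconditional text governs, the per-group SAE counts cover all causes. If the 8.2 wording governs, they cover related events only. Section 11.1 refers to events observed, which does not choose between the two.

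**Step 4: scale**

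The documents give no adverse event rate, so the number of events affected cannot be estimated. For scale only, take the percentage as patients with an event divided by the 23 enrolled per arm (an assumption, since 11.1 states no denominator). One patient left out lowers that arm's figure by 1/23 = 0.043, or 4.3 percentage points.

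The 19 evaluable and 23 enrolled patients per arm and the power of 0.90 are not affected.

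**The case against.** The strongest reply is that the word only occurs once, about reporting of SAEs, and that the rest of the protocol supports full documentation. Sections 6.5.1.1 and 8.1 and the calendar have adverse events documented or assessed without a filter. Section 9.1 has staff keep all responses from the calls, and Section 9.2 has patients report adverse effects each week. Section 11.1 is descriptive, sits under acceptability and concerns serious events. Safety is neither a primary nor a listed secondary objective. The protocol also argues for light oversight on the grounds of low risk and a device already cleared for marketing.

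Most of this stands, and it rules out two stronger readings that a reader might infer.

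- That only related events are ever recorded. The unfiltered statements, and the rule in 9.1 that responses are kept, prevent this from being established. The protocol is inconsistent here; it is not settled against capture.
- That the comparison between arms is biased. No assessor is named, and arm keys stay sealed until the block is unblinded (Section 6.4). Whether those judging relatedness are blinded is not stated. A filter on cause could remove events from both arms, and nothing in the documents shows that it would remove more from one.

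The reply does not remove the SAE conflict. Low expected risk may justify a simple reporting rule, but it does not make two opposite rules workable.

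**Conclusion.** The conflict between 8.1 and 8.2 on SAEs judged unrelated is plain on the page and needs no assumption. The inconsistency on capture of unrelated adverse events is also real, but which reading was intended cannot be determined.

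The consequence for the 11.1 counts is conditional: it arises only if the 8.2 wording governs and is read as limiting what is entered. The number of events at stake is unknown. The change should be made because staff cannot comply with both SAE rules and because the content of the only planned per-group adverse event output is undefined. It does not bear on the primary endpoint.

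**What to change.** - Reconcile 8.1 and 8.2 into a single SAE-to-IRB rule, consistent with the institutional standard, that states which events are reported and when.
- State in 8.1 and 8.2 that every adverse event and SAE elicited at the scheduled contacts is recorded, whatever the suspected cause. Store seriousness and relatedness as fields.
- Name the role that judges relatedness, say whether that person is blinded, and have the judgement made before the block is unblinded. Section 6.5.1.1, item 12, opens the block at the end of the open-label phase, so events first reported at weeks 12 or 16 may be judged afterwards and should be marked as such.
- In 11.1, tabulate all-cause and related events by randomised arm for the 4-week blinded phase, and give the denominator. Show the open-label phase separately, because every patient then receives a functional device and the sham contrast no longer exists.

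The cost is protocol wording, submitted as an amendment for IRB approval under Section 10.1, plus the added data fields and a few more entries. Patients are already asked about adverse events every week, so no extra contact is needed.

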9.1. Data Management

All information will be collected by study staff through zoom conversations with patients. She will maintain all responses on computer programs using only de-identified patient numbers.

All study data will be reviewed for completeness and accuracy by the Principal Investigator.

9.2. Monitoring

Each week, patients will communicate with the study coordinator to check in and report adverse effects. At the start of the study, at the end of the experimental phase and at the conclusion of the study, quality of life surveys will be conducted by Zoom. Four and eight weeks after the study is completed, patients will be contacted to report their pain scores.

TENS for Neuropathic Pain in NMOSD

Principal Investigator: [name], PhD

10. Administrative Procedures

10.1. Protocol Amendments

Any changes to the protocol will be made in the form of an amendment and must be approved by the IRB before implementation. The Principal Investigator (or his designee) is responsible for the coordination and development of all protocol amendments.

10.2. Informed Consent

Human subjects will be recruited through the Mass General NMOSD Clinic. This clinical trial will be posted through clinicaltrials.org and on The NMO Clinic's Facebook page. Those patients who seek participation from outside of the Massachusetts General Brigham network are eligible to be screened. On-line consent forms will be provided to interested patients after an initial intake phone call. The consent form RedCap (or other approved IRB platform) link will be emailed to the patient and then discussed with the study coordinator over a Zoom call. The Principal Investigator or the study coordinator will explain to each patient the nature of the study, its purpose, procedures involved, expected duration, potential risks and benefits. Each patient will be informed that participation in the study is voluntary, that he/she may withdraw from the study at any time, and that withdrawal of consent will not affect his/her subsequent medical treatment. This informed consent will be given by means of an on-line statement and has been approved by the IRB. No patient will enter the study before her informed consent has been obtained. In accordance with the Health Insurance Portability and Accountability Act (HIPAA), the informed consent document (or a separate document to be given in conjunction with the consent document) will include a participant authorization to release medical information to the study sponsor and supporting agencies and/or allow these bodies, a regulatory authority, or Institutional Review Board access to subjects' medical information that includes all hospital records relevant to the study, including subjects' medical history. The PI or study coordinator will file the signed consent forms.

10.3. Ethics and Good Clinical Practice

This study must be carried out in compliance with the protocol and Good Clinical Practice, as described in:

1. ICH Harmonized Tripartite Guidelines for Good Clinical Practice 1996.
2. US 21 Code of Federal Regulations dealing with clinical studies (including parts 50 and 56 concerning informed consent and IRB regulations).
3. Declaration of Helsinki, concerning medical research in humans (Recommendations Guiding Physicians in Biomedical Research Involving Human Subjects, Helsinki 1964, amended Tokyo 1975, Venice 1983, Hong Kong 1989, Somerset West 1996).

The investigator agrees to adhere to the instructions and procedures described in it and thereby to adhere to the principles of Good Clinical Practice.

TENS for Neuropathic Pain in NMOSD

Principal Investigator: [name], PhD

10.4. Regulatory Authorities

10.4.1. Institutional Review Board

Information regarding study conduct and progress will be reported to the Institutional Review Board (IRB) per the current institutional standards.

11. Statistical Plan

11.1. Acceptability

Counts and percentages will be used to assess acceptability based on adherence to treatment schedule. We will report the number and percent of patients in each group who are able to complete all treatments. A chi-square test for independence of group by dichotomous outcome will be performed to assess differences between the two groups. In the event that the expected frequencies are < 5 , Fisher's exact test will be performed. While no serious adverse events have been reported with use of Scrambler or other TENS therapies in the NMOSD patient population, the numbers and percent observed for each group will be reported.

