2.1. Scheme

Patients will be randomized 1:1 to receive treatment daily for 4 consecutive weeks versus sham, followed by an open-label phase for additional 4 consecutive weeks.

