2.3. Secondary

Six secondary objectives are intended to collect additional information about the potential benefit of QUELL FLEX:

- A. The difference in pain scores at the end of the open label phase compared to the end of the initial blinded phase.
- B. A change in the “worst” pain score in the treatment arm vs. the sham arm between the baseline screening call and week 4; and the change in the “worst” pain from baseline to week 8 for all subjects.
- C. A change in the “average” pain score in the treatment arm vs. the sham arm between the baseline screening call and week 4; and the change in the “average” pain from baseline to week 8 for all subjects.
- D. The number of patients who withdraw because of poor compliance. We expect a higher withdrawal and non-compliance rate in the sham group.
- E. Quality of life surveys will be conducted before and after the treatment phase and at the end of the study to determine if the QUELL FLEX treatment impacts overall quality of life.
- F. Reduction in pain medication use over the course of the study.

TENS for Neuropathic Pain in NMOSD

Principal Investigator: [name], PhD

3. Hypotheses

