3.2. Secondary

- QUELL FLEX therapy is an acceptable treatment measured by compliance and patient survey.
- Patients who were randomized initially to the sham arm will show a reduction in pain score after crossing over into the open label arm. In contrast, the patients in the treatment arm will not necessarily show additional benefit after rolling over in the open label arm.
- The “average” and “worst” pain scores will decline in the treatment arm and not necessarily in the sham arm.
- As pain is a primary driver of quality of life, quality of life will improve with treatment compared to sham.
- Patients for whom QUELL FLEX works well may choose to reduce their intake of pain medications.

4. Background and Rationale

4.1. Etiology and current treatment of central neuropathic pain in patients with neuromyelitis optica spectrum disorder

Neuromyelitis optica spectrum disorder (NMOSD) is an autoimmune disease of the central nervous system (CNS) that preferentially causes recurrent inflammatory attacks in the optic nerves and spinal cord, leading to blindness, paralysis and death. Despite these devastating consequences of the disease, patients have reported that pain is among the most prevalent and debilitating symptoms.

In particular, central neuropathic pain (CNP) is pervasive, severe, intractable to treatment, and affects 62-91% of patients with NMOSD. CNP is described as agonizing burning, stabbing, shooting, tingling or squeezing

Figure 1. Cross-section of the spinal cord depicting spinal tracts.

From:

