6.5.1.1. Treatment Days

1. Prior to initiation of Quell therapy, patients will be asked to rate their pain on the Numerical Pain Scale and will complete a Short Form-36 Health Inventory (SF-36).
2. All training on the use of the device will be conducted remotely through Zoom.

TENS for Neuropathic Pain in NMOSD

Principal Investigator: [name], PhD

3. Patients will be shipped a QUELL FLEX device. It will either be a functional QUELL FLEX device for the treatment arm or a non-functional QUELL FLEX device in the sham arm. All of the lights, charging equipment, and app connectivity will be the same. The only difference is that the non-functional sham devices will administer an electrical current for only 2 minutes each at the top of a treatment hour, at 30 minutes and at 58 minutes, as opposed to for the full hour when the device is engaged.
4. Patients will be informed that we are conducting a number of different treatment paradigms – some of them have high frequency waves that are not perceptible, and some have lower frequency waves that may be transiently perceptible. In addition, we will re-inform them there is a sham arm.
5. The electrodes will be placed on patients on the back in the dermatome of the most painful area. The intensity of the stimulus is increased until the patient can first feel some sensation associated with the electrodes. Script: “Tell me when you feel something.”
6. Stimulation intensity will be increased until a maximum threshold is tolerated without being painful.
7. Once the intensity is at its maximum setting, the study coordinator will evaluate the level of pain. If the patient feels a constant burn, single sting or feeling of discomfort, the electrodes will be repositioned. The exact electrode positioning will depend on the delimitation of the surface pain area, and analgesic response of the patient.
8. Once satisfactory electrode placement and stimulus intensity is determined, therapy is maintained for at least an hour per day for 4 weeks (both treatment and sham groups).
9. Patients will report pain scores weekly throughout experimental period while on a zoom call with the trial researcher. Patients will again complete all measurement tools and pain ranking at end of treatment.

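### Acceptability is tested only as completing all treatments, which under daily use fails a patient for one missed day and discards information on the between-arm compliance difference

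*Combined protocol and SAP*

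**What the plan says.** Section 11.1 opens with a general aim: "Counts and percentages will be used to assess acceptability based on adherence to treatment schedule". The specific outcome is "the number and percent of patients in each group who are able to complete all treatments", and the test is "A chi-square test for independence of group by dichotomous outcome will be performed to assess differences between the two groups", with Fisher's exact test when expected frequencies fall below 5. No other acceptability outcome is given a test.

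The schedule is in section 2.1, "Patients will be randomized 1:1 to receive treatment daily for 4 consecutive weeks versus sham", and in section 6.5.1.1, which asks both arms for at least an hour a day over the 4 weeks. Four open-label weeks follow.

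Compliance appears in three other places:

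- Section 6.8.1 lists non-compliance among the reasons for stopping protocol treatment and gives as an example "not using the device more than 75% of the study duration".
- Section 2.3, objective D, is "The number of patients who withdraw because of poor compliance", and anticipates more withdrawal and non-compliance under sham.
- Section 3.2 states that acceptability is "measured by compliance and patient survey", with no threshold.

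The plan does not define a completed treatment, does not say whether the open-label weeks count, and does not say how use is recorded.

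**The concern.** Objective D makes a between-arm difference in compliance a stated expectation. The one test that section 11.1 provides treats a patient who missed a single day and a patient who missed twenty as the same, because both did not complete all treatments. Differences among non-completers then contribute nothing to the comparison.

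The completion percentage also says little about how much the device was used. It can look poor when average use is high. Because the only numeric compliance level in the protocol is 75%, a reader of the results would see two figures on different scales with nothing to connect them.

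**Working it through.** **Inputs from the documents.** Daily use for 4 weeks (2.1, 6.5.1.1); 75% (6.8.1); 23 patients per arm (11.2). The plan states no expected adherence, power or alpha for acceptability, so there is no figure of its own to reproduce. All adherence values below are assumptions, and tests are two-sided at 0.05.

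**What the literal rule means.** 4 × 7 = 28 days, so 27/28 = 96.4% fails. If both phases count, the bar is 56 of 56.

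**What the 75% wording means.** 0.75 × 28 = 21 days. One reading is use on no more than 21 days. The other is non-use on more than 21 days, that is, use on 6 days or fewer. On either reading a patient with 22 to 27 days (79% to 96%) falls outside the non-compliance example, yet is a non-completer under the literal reading of 11.1. If the reference is 8 weeks, the cut is 0.75 × 56 = 42 days. The wording also does not say days or hours.

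**Share completing all 28 days.**

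- If every patient has the same independent daily probability p, the share is p^28.
- With between-patient spread (beta-binomial, mean m, precision 10), it is the product over i = 0 to 27 of (10m + i)/(10 + i).

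| Assumed daily use | All 28, patients alike | All 28, with spread | More than 21 of 28, alike | More than 21 of 28, with spread |
|---|---|---|---|---|
| 97% | 42.6% | 66% | >99.9% | 98.1% |
| 95% | 23.8% | 50% | >99.9% | 96.1% |
| 90% | 5.2% | 24% | 98.2% | 88.5% |

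**Power, 23 per arm, beta-binomial.** Fisher's exact test on all 28 against a rank-sum test on sessions completed:

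| Mean use by arm | Precision | All 28 (Fisher) | Sessions completed (rank-sum) |
|---|---|---|---|
| 0.93 / 0.80 | 10 | 0.72 | 0.97 |
| 0.90 / 0.80 | 10 | 0.34 | 0.81 |
| 0.95 / 0.90 | 10 | 0.33 | 0.55 |
| 0.93 / 0.80 | 2 | 0.63 | 0.75 |

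Repeat simulation runs move these figures by up to about 0.03. With no true difference the rank-sum test rejected about 5% of the time.

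**Effect of the plan's choice of test.** Section 11.1 uses chi-square unless expected counts are below 5. Summing the two binomial probabilities (23 per arm, completion probabilities from the product formula) over all tables that the plan's rule would reject, with chi-square uncorrected for continuity, gives 0.78, 0.36, 0.44 and 0.73 in the same row order. With the continuity correction the results match Fisher. So the gap narrows in every row, and in the last row it almost closes.

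**A 75% cut instead.** In the first scenario, Fisher power is about 0.62 for more than 21 of 28 and about 0.51 for at least 21. Both are below the 0.72 for all 28.

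**The case against.** **Is there a contradiction?** A reader might infer that 11.1 contradicts 6.8.1. It does not. Section 6.8.1 gives a reason to stop protocol treatment and 11.1 gives an analysis outcome. A patient can miss a few days, stay on treatment and be counted as a non-completer with both rules in force. What stands is that the measures are not aligned and that the 75% wording is ambiguous.

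**Is 28 of 28 the plan's rule?** The figure 28 appears nowhere in the documents. The phrase could mean finishing the 4-week course, or 56 days over both phases. This objection stands, and it is why the point is worded as the literal reading of an undefined outcome.

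**Would a well-used device be reported as mostly not completed?** A reader might infer this, but it holds only under some assumptions. With between-patient spread, 66% complete at 97% daily use and about half at 95%. The plan also has a patient survey (3.2), a count of compliance withdrawals (objective D) and a general statement on adherence counts (11.1), so the completion percentage would not stand alone.

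**Is the power gain real?** The scenarios are assumed and the gain ranges from large to negligible. The session count came out ahead in each scenario, although at precision 2 against an uncorrected chi-square (0.73 vs 0.75) the difference is within simulation error. No power is claimed for this secondary outcome, and a completion percentage is a conventional, readable summary. That is a reason to keep reporting it, not a reason to make it the only thing tested.

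**Are the data there?** The documents do not plan to record days of use. App connectivity is mentioned in 6.5.1.1, but not usage logging. This stands and adds a small cost.

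**Conclusion.** The point holds as a cheap improvement to a secondary analysis. The only tested acceptability outcome is an undefined all-or-nothing completion. On the literal daily reading it fails a patient for one missed day in 28 and discards the graded information on the compliance difference that objective D expects. It is also not aligned with the protocol's single numeric compliance level.

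The size rests on assumptions outside the documents: daily use of 90% to 97%, between-patient spread at precision 10 or 2, and mean differences of 0.05 to 0.13 between arms. Under these, the rank-sum test on sessions gains 0.12 to 0.47 in power over Fisher on all 28, and less over an uncorrected chi-square. The direction was the same throughout; the amount should not be relied on. Nothing here bears on the primary pain comparison.

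**What to change.** In section 11.1:

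- Make the tested acceptability outcome the number of scheduled blinded-phase daily sessions completed per patient, out of 28, compared between arms by a rank-sum test.
- For this outcome, count days after discontinuation as not completed. Define a completed session.
- Report the number and percentage completing all sessions descriptively, without a test.

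Moving the dichotomy to 75% is not a substitute, since in the first scenario it loses power against the all-28 outcome.

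Add one question on days of use to the weekly Zoom calls that 6.5.1.2 already schedules. Both the 11.1 outcome and the 75% wording already require this information.

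Reconcile objective D (2.3), the hypothesis in 3.2, section 6.8.1 and section 11.1 so that one stated compliance definition feeds all the counts: days or hours, 4 or 8 weeks, and which way the 75% phrase is read. Which discontinuation rule applies is for the sponsor. Because 6.4 unblinds in blocks of four during the study, settle the definition before the first block is unsealed.

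The cost is SAP and protocol wording, one added question per weekly call, and a headline that is less simple than a completion percentage.
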